#### V. Risks and Benefits

#### Possible Risks of OnabotulinumtoxinA:

Side effects and discomforts that have been observed in patients who have received treatment with this study medication for their OAB symptoms include:

Most Frequent (occurring more than 10% of the time):

 weakness of the bladder muscle resulting in difficulty in urination or an inability to urinate or empty the bladder (urinary retention) for an extended period (less than a month in most cases, but could be longer)

Less Frequent (occurring from 1% to 10% of the time):

- constipation
- Rare (occurring less than 1% of the time):
- generalized weakness

### Possible Risks of Injection Procedure:

As with any injection, patients may experience local pain/soreness, bleeding, bruising, infection, and/or swelling. Some people feel faint or pass-out when being injected with medications.

The following side effects have been observed in patients who have received treatment with this study medication for their OAB symptoms:

Most Frequent (occurring more than 10% of the time):

- urinary tract infection
- Less Frequent (occurring from 1% to 10% of the time):
- blood in the urine
- difficulty or painful urination

Rare (occurring less than 1% of the time)

- temporary bleeding at the injection site resulting in a blood clot in the bladder tissue
- urosepsis (an infection that occurs when urinary tract infection spreads to the bloodstream)

The following side effects have not been observed previously with study medication injections but could possibly happen:

Less Frequent (occurring from 1% to 10% of the time):

- permanent tissue damage from repeated injections
- accidental bladder wall puncture resulting in onabotulinumtoxinA introduction into abdominal space or near-by structures
- injury from the cystoscope resulting in temporary urethral swelling, urethral injury, blockage of urine flow, or overstretching of the bladder
- increased blood pressure
- headache
- decreased heart rate

Rare (occurring less than 1% of the time):

- local pain/soreness
- bleeding
- bruising
- infection
- swelling
- feeling faint or passing out when being injected

#### Possible Risks of Cystoscopy

Less Frequent (occurring more than 1% but less than 10% of the time):

- discomfort or pain
- cramps
- infection
- painful or difficult urination

Rare (occurring less than 1% of the time):

- bleeding (blood in urine)
- inability to pass urine after the procedure
- trauma
- urinary tract infection
- puncture of the bladder
- temporary swelling or injury to the urethra
- overstretching of the bladder
- a change in urinary frequency
- urgency in urination, including urgency resulting in episodes of urge incontinence

#### **Risks of Antibiotic (Medicine to Prevent Infection)**

Less Frequent (occurring more than 1% but less than 10% of the time):

• Diarrhea

- Nausea and vomiting
- Stomach cramping

Rare (occurring less than 1% of the time):

- Headache
- Itching
- Rash
- Allergic reaction

There may be no direct benefit in taking part in this study. Symptoms of OAB may improve, but this cannot be guaranteed. Information gained from the results of this study may be of benefit to others in the future, with a similar medical condition.

#### VI. Eligibility Criteria

Inclusion criteria:

- Women and men  $\geq$  18 years of age
- Self-reported failed conservative care of behavioral modifications and/or oral medications for the treatment of OAB
- Average urinary frequency of ≥ 8 voids per day as recorded on initial 3-day voiding diary
- Self-reported bladder symptoms > 3 months
- Discontinued antimuscarinics/beta-3 agonists for 2 weeks prior to study enrollment.
   May restart antimuscarinics/beta-3 agonists if indicated 6 weeks after Botox injections.
- Previous onabotulinumA injection at least three months prior to study enrollment
- Capable of giving informed consent
- Capable and willing to follow all study-related procedures

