#### IV. Methodology

Although a pilot study has been published regarding injection sites as few as one for 100 U of BTX, there has not been a randomized study comparing fewer injections sites to what is commonly practiced (ten injection sites).

Patients diagnosed with OAB and that have failed first and second line treatments will be presented with all third line therapies including BTX, SNS, and PTNS. Patients choosing BTX will be offered an opportunity to enroll in this study. If patients are already clinical responders and currently receiving BTX therapy, they are eligible for randomization if they choose to participate in the study. If they had prior BTX and were clinical non-responders they will not be eligible. Clinical non-responders are patients who previously reported no subjective improvement in their symptoms by 3 months after their injection. If a patient was an initial responder (with subjective improvement reported by the patient), and the effect has since worn off, the earliest they can receive re-injection will be 3 months after their initial injection. All repeat injections will be done at with a minimum of 3 months in between injections.

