#### VII. Data Analysis

**Statistical Analysis** 

#### Primary Effectiveness

The primary efficacy endpoint is defined as at least a 50% reduction in number of urgency related incontinence episodes at 3 months. The number of urgency incontinent episodes per day is measured as the average of two, 3-day, consecutive bladder diaries. Patients shall be classified as treatment successes or treatment failures based on this criterion.

The primary hypothesis is that the proportion of patients who are treatment successes with BTX-3 is non-inferior with a margin of 15% to that with BTX-10 at 3 months.

 $H_{o}: p_{BTX-3} \le p_{BTX-10} - 0.15 \text{ vs}$   $H_{a}: p_{BTX-3} > p_{BTX-10} - 0.15$ 

In the hypothesis equations, 0.15 is the clinical equivalence margin for the non-inferiority test of this hypothesis.

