#### Sample Size and Power Calculation

One hundred seventy-eight (178 patients will be randomized in this study, 89 per group to achieve 80% power to detect a non-inferiority margin difference between the group proportions of 0.15. The reference group (BTX-10) proportion is 0.85. The treatment group proportion (BTX-3) is assumed to be larger than 0.70 under the null hypothesis of inferiority. The power was computed for the case when the actual treatment group proportion is 0.85, that is both BTX-10 and BTX-3 had the same response rate of 0.85. The test statistic used is the one-sided Z test with a Type I error rate of 0.025.

Power	N1	N2	N	Reference (BTX-10) Responder Rate	BTX-3 Responder RatejH0	BTX-3 Responder Rate Ha
0.8	147	147	294	0.7	0.55	0.7
0.85	168	168	336	0.7	0.55	0.7
0.9	197	197	394	0.7	0.55	0.7
0.8	131	131	262	0.75	0.6	0.75
0.85	150	150	300	0.75	0.6	0.75
0.9	176	176	352	0.75	0.6	0.75
0.8	112	112	224	0.8	0.65	0.8
0.85	128	128	256	0.8	0.65	0.8
0.9	150	150	300	0.8	0.65	0.8

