#### Table Non Inferiority Sample size; Margin of 0.15 and expected delta=0

Power	N1	N2	N	Reference (BTX-10) Responder Rate	BTX-3 Responder Rate H0	BTX-3 Responder Rate Ha
0.8	89	89	178	0.85	0.7	0.85
0.85	102	102	204	0.85	0.7	0.85
0.9	120	120	240	0.85	0.7	0.85
0.8	63	63	126	0.9	0.75	0.9
0.85	72	72	144	0.9	0.75	0.9
0.9	85	85	170	0.9	0.75	0.9

Table Non Inferiority Sample size; Margin of 0.15 and expected delta=0

At 3 months, the percentage of patients who are successfully treated will be computed for each treatment group. Patients who exit the study early citing reasons of inadequate urge or incontinence reduction will be included in this analysis as *treatment failures*. Treatment-failure patients are otherwise known as *non-responders*.

The success rate in the BTX-3 group will be compared to that in the BTX-10 group using a non-inferiority at  $\alpha$  = 0.025 and  $\delta$  =.15 as shown earlier in this protocol.

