#### Data analyses

A biostatistician will perform all statistical analyses using SAS or similar statistical software. Descriptive statistics will be calculated. A completer analysis will be conducted for those who finish the study per protocol. The primary endpoint will be assessed comparing incontinence episodes per day at 3 months after BTX injection. This comparison will also be made for all other visits using t-tests or chi-square tests, as appropriate.

Secondary endpoints will include adverse events and comparisons between 3-site and 10-site groups looking at the GRA responses between 3-site and 10-site groups at 3 months (± 14 days) post injection, 3-day voiding diary and OABq-SF and ICIQ-SF at 3 months (± 14 days) post-injection. We will also compare post-injection VAS scores to assess for tolerability, satisfaction, and pain. Changes from baseline will also be analyzed. This comparison will also be made for all other visits using appropriate statistical tests.

In addition to a completer analysis, we also plan on conducting an intent to treat analyses which will identify any subject not assessed at 3 months after the first BTX injection as a treatment failure. In order to assess for all possible situations, 4 different scenarios will be run: 1) All dropouts will be considered non-responders for both groups 2) All dropouts will be considered responders for both groups, 3) Dropouts in the BTX 10 group will be considered responders and those in the BTX 3 group, non-responders, and 4) Dropouts in the BTX 10 group will be considered non-responders while those in the BTX 3 group, responders.

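### The responder endpoint needs a baseline urgency incontinence episode, but no entry criterion requires one and no rule expressly classifies a patient who has none

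*Combined protocol and SAP*

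**What the plan says.** Section VII, Primary Effectiveness, defines the endpoint: "The primary efficacy endpoint is defined as at least a 50% reduction in number of urgency related incontinence episodes at 3 months". It adds: "Patients shall be classified as treatment successes or treatment failures based on this criterion". The daily count there is the mean of two consecutive three-day diaries.

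Section IV recruits "Patients diagnosed with OAB and that have failed first and second line treatments". In section VI the one diary-based inclusion criterion is "Average urinary frequency of ≥ 8 voids per day as recorded on initial 3-day voiding diary". The other symptom criterion asks for more than 3 months of bladder symptoms and does not name incontinence. No exclusion criterion removes a patient without leakage. Section IV and its schedule describe a single three-day diary at screening.

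Two rules go beyond the 50% criterion. Under the sample-size tables: "Patients who exit the study early citing reasons of inadequate urge or incontinence reduction will be included in this analysis as" treatment failures. Under Data analyses (and in section IV), the intent-to-treat analysis will "identify any subject not assessed at 3 months after the first BTX injection as a treatment failure", with four scenarios for dropouts. Neither rule concerns a zero baseline.

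On size, 178 "patients will be randomized in this study, 89 per group to achieve 80% power", and "The reference group (BTX-10) proportion is 0.85". The margin is 0.15 and the test is a one-sided Z test at 0.025.

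Section III and the Data analyses section also call a comparison of episodes per day at 3 months primary.

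**The concern.** A percentage reduction has no value when the baseline is zero. A patient with eight or more voids a day and no leakage meets the written criteria, is randomised, attends at 3 months, and must then be called a success or a failure on a quantity that cannot be computed.

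Reasonable analysts could handle that patient differently. If success means that a reduction was shown, zero to zero is a failure. If the reduction is computed as a ratio, the result is undefined and the patient may drop out of the analysis. If success is coded as a follow-up count of no more than half the baseline count, zero to zero is a success. These choices can give different denominators, response rates and power, and the plan does not expressly choose among them. A choice made once outcomes by arm are visible could look driven by the result. The trial also plans an efficacy and futility look once 25 patients per arm are randomised, so the choice could be needed early.

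The number randomised equals the tabulated requirement exactly, so it has no reserve for patients who cannot be scored.

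**Working it through.** **Inputs from the plan** (Primary Effectiveness; Sample Size and Power Calculation): 89 per arm, response rate 0.85 in both arms, margin 0.15, one-sided alpha 0.025.

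**Assumed, not in the documents:** a share f of patients dry at baseline, equal in both arms, at 5%, 10%, 20% and 30%.

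**Formula** (unpooled Z test, equal true rates p in both arms):

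power = Φ( 0.15 / √(2p(1−p)/n) − 1.96 )

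**1. The plan's own figure.** With p = 0.85 and n = 89, the standard error is √(2 × 0.1275/89) = 0.0535. Then 0.15/0.0535 = 2.802, 2.802 − 1.96 = 0.842, and Φ(0.842) = 0.800. Exact enumeration of the same test gives 0.801. The stated 89 per arm is correct for these inputs.

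**2. Dry patients left out of the responder analysis.** n = 89(1−f), rounded, with p = 0.85 in the analysed set. Example at f = 10%: n = 80, standard error √(0.255/80) = 0.0565, 2.657 − 1.96 = 0.697, power 0.757.

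**3. Dry patients scored as failures, with 0.85 taken as the rate among incontinent patients** (a second assumption). n = 89 and p = 0.85(1−f). Example at f = 10%: p = 0.765, standard error √(2 × 0.1798/89) = 0.0636, 2.360 − 1.96 = 0.400, power 0.655.

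| f | n per arm if left out | power, left out (exact) | total N to keep 89 scorable per arm | p if scored as failures | power, scored as failures |
|---|---|---|---|---|---|
| 0% | 89 | 0.800 (0.801) | 178 | 0.850 | 0.800 |
| 5% | 85 | 0.782 (0.784) | 188 | 0.808 | 0.718 |
| 10% | 80 | 0.757 (0.766) | 198 | 0.765 | 0.655 |
| 20% | 71 | 0.706 (0.714) | 224 | 0.680 | 0.573 |
| 30% | 62 | 0.648 (0.652) | 256 | 0.595 | 0.531 |

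Total N is 2 × 89/(1−f), with the per-arm number rounded up.

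**4. Dry patients scored as failures, with 0.85 taken as the rate among everyone enrolled.** Then p = 0.85 and n = 89, so power stays at 0.800. The rate this implies among incontinent patients is 0.85/(1−f): 0.895 at f = 5%, 0.944 at 10%, 1.00 at 15%. Above 15% this reading is impossible.

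**5. Dry patients all scored as successes, for contrast.** With 0.85 among incontinent patients, p = f + 0.85(1−f), and nominal power is 0.817, 0.834, 0.869 and 0.904 at the four values of f. This supposes that no dry patient is scored a failure, even one who leaks at 3 months.

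**6. Type I error.** With the true deficit in the analysed set at 0.15, the exact rejection probability lies between about 2.4% and 2.8% under exclusion, failure scoring and success scoring alike.

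**The case against.** **The rule is already there.** The classification is binary, and a patient who shows no 50% reduction is not a success. That is the most literal reading. It remains an inference, and it labels a patient who stayed dry a treatment failure. What is missing is an express rule for a case that the entry criteria allow.

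**Dry patients are not useless to the primary analysis.** A reader might infer that they cannot inform it at all. The documents do not support that: section III and the Data analyses section also treat episodes per day at 3 months as primary, and a dry patient contributes to that comparison. The problem is confined to the responder endpoint.

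**The size is assumed.** This stands. If nearly all enrolled patients leak at baseline, almost nothing changes; at 5% dry, leaving them out costs about 2 points of power. The exclusion losses also arise under a rule that the plan does not contain, so for patients already enrolled they are partly the price of the remedy. The larger losses under failure scoring need 0.85 to describe incontinent patients, whereas the text attaches it to the reference group without qualification.

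**False positives.** A reader might infer that scoring dry patients inflates the type I error. It does not for the null hypothesis in the plan. Scoring dry patients alike in both arms dilutes a deficit confined to incontinent patients, but the plan sets no separate hypothesis or margin for that subgroup.

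**Restricting eligibility is partly a preference.** This also stands. The trial addresses refractory OAB, and tolerability matters for every enrolled patient. An express zero-baseline rule would close the classification gap without changing who is enrolled.

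**Conclusion.** The concern holds for the responder endpoint. No criterion requires a baseline episode, and no text expressly classifies a patient without one; both follow directly from the documents. The size does not. With an assumed 5% to 30% dry, power runs from 78% to 65% if they are left out, and from 72% to 53% if they are scored as failures and 0.85 describes incontinent patients. It stays at 80% if 0.85 already covers everyone under failure scoring.

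Two further inferences should be resisted. The sample-size calculation is not wrong; it reproduces exactly. Nor do the documents show that the trial is underpowered, because they give no dry share. This is a cheap improvement.

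**What to change.** Add to section VI an inclusion criterion: a sponsor-chosen minimum of at least one urgency incontinence episode at baseline. State which diary measurement defines it, and reconcile the single initial three-day diary in sections IV and VI with the two consecutive diaries in the endpoint definition; a patient can be dry on one diary and not on the next.

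For anyone already enrolled dry, state before any comparison by arm, including the look at 25 per arm in section VIII, that the primary responder analysis uses all randomised patients with at least one baseline episode, analysed as randomised. Apply the not-assessed-is-failure rule and the four dropout scenarios to that set, and restate the power for its size. Keep dry patients in the episodes-per-day, safety, VAS, GRA and questionnaire analyses.

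If the sponsor prefers to keep dry patients eligible, write an express zero-baseline rule and state that the 0.85 and the 0.15 margin refer to all patients under that scoring.

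Cost: one eligibility line and a short SAP paragraph; a screening diary is already collected. The downsides are somewhat slower recruitment, a primary claim limited to OAB with incontinence, and a responder set narrower than all randomised if anyone has already been enrolled dry.

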Consent to send out pre-screening activities may be done by telephone script with all elements of information sheet included. Participant agreement is consent to send prescreening activities. Once the participant is present for enrollment visit, a formal consent will be performed for study participation. Informed consent will be obtained from all patients prior to conducting any study activities. Consented patients will complete the OAB-g SF, ICIQ-SF, 3-day voiding diary and enrollment guestionnaire (demographics, medical history, concomitant medications, etc.) prior to study enrollment. A urinalysis (UA) will be collected at this visit as well and a urine culture (UCx) will be performed, if necessary. If the patient meets the eligibility criteria, they will be randomized (1:1) into the 3-injection site group or the 10injection site group. We plan on performing a stratified randomization so the number of BTX naïve and previous BTX responder patients will be equivalent in both arms in order to minimize selection bias. Patients will be blinded to the number of injections they will receive. Adverse events and concomitant medications will be assessed at each follow-up visit. A diary will also be completed, collected and reviewed at each follow-up visit. GRA will also be gathered at each follow up visit. Visual Analog Scores will be gathered at the end of the injection visit to assess for patient satisfaction, pain, and tolerability.

Patients will be asked to remain off any oral anticholinergic or beta-3 agonist medications, PTNS therapy, or any neuromodulation throughout the entirety of the study.

Patients will follow up two weeks post-injection (±7days) for an office visit. OAB-q SF, GRA, ICIQ-SF, 3-day voiding diary, UA and post void residual (PVR) will be collected. If necessary, a UCx will be ordered for evaluation.

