At 3, 6, 9, and 12 months post-injection (± 14 days), patients will return for follow-up appointments. OAB-q SF, GRA, ICIQ-SF, patient satisfaction, 3-day voiding diary, and UA will be collected. If necessary, a UCx will be ordered for evaluation. We will also assess for adverse events and concomitant medications at each of these visits. Specific adverse events we will be tracking include urinary retention (inability to void), elevated PVR of greater than 300 cc, UTI, excessive bleeding at injection sites that requires cautery, and systemic BTX effects (systemic weakness). If at any visit the patient is found to have a UTI, they will be prompted to repeat that visits questionnaires and 3-day diary at an unscheduled visit once the prescribed UTI treatment has been completed. At the unscheduled visit AEs will be reviewed and a clinical decision will be made by an investigator if UTI symptoms are still present after treatment completion. The unscheduled visit will occur at the urology research clinic.

If a repeat botox injection is given at the 3, 6, or 9 month visit, the subject will have a 2 week follow up visit identical to visit 3 in the schedule of events before continuing to be followed every 3 months.

While in-person visits are preferable, if the patient is unwilling or unable to attend a study visit (specifically visits 4-7) they will not be withdrawn from the study. In order to assess patient safety and provide continuing follow-up, the patient may be contacted by phone and/or mail. If necessary, study information may be collected by either or both of these methods; phone (current medications, AE assessment) and/or mail (questionnaires, voiding diary). If a patient requires a remote visit, they may complete at least one, but not all visits remotely.

	Consent and Screening	Enrollment and Treatment	2 Weeks Post-BTX Visit (±7 days)	3 Months Post-BTX Visit d (± 14 days)	6 Months Post-BTX Visit d (± 14 days)	9 Months Post-BTX Visit d (± 14 days)	12 Months Post-BTX Visit (± 14 days)
	Visit 1	Visit 2	Visit 3	Visit 4	Visit 5	Visit 6	Visit 7
Consent	X						
Eligibility	X						
Demographics, Medical History	X						
OABq-SF ICIQ-SF	X		X	X	X	X	X
3-day Voiding Diary	X		X	X	X	X	X
Urinalysis, Urine Culture as needed	X	X	X	X	X	X	X
Pregnancy test before injection as needed a	X	X		X	X	X	
Post void residual (PVR) ♭			Х				
BTX injection		X					
Repeat BTX				X	X	X	

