The patient will receive BTX injections according to the group to which they have been randomized. If the patient has been randomized into the 3 injection group, they will receive an additional 7 "sham injections" with the needle retracted (no break in the mucosa). We decided on this as a sham treatment instead of actually puncturing the mucosa without injecting BTX because the point of our study is also to assess patient satisfaction and tolerability as well as rates of adverse events (ie hematuria and UTI). In order to do this, we want to puncture the mucosa less (3 vs 10). For the 3 injection group, every 3rd injection will be an actual mucosal penetration and injection (for 3 total injections containing BTX) in order to keep the patient blinded as best as possible. The 3 BTX injections will still be placed in the location as outlined in the diagram (Figure 1). The other 7 injection's will be verbally emphasized by the clinician but will not have mucosal penetration with the needle. It has been our experience that patients have variable sensation with needle penetration, sometimes no or minimal sensation to a clear sensation of a needle poke. The provider will verbalize the injection number to the patient whether it is a true injection or not in order to keep a believable pace. All patients will be told "This is injection #1. This is injection #2. This is injection #3." and so forth. Care will also be taken to prevent the patient from seeing the syringe so they cannot guess the arm of the study to which they were randomized. All patients will think they are receiving ten injections. Post-injection, the patient will be evaluated for hemostasis. Cautery will be used if deemed necessary by the physician. If hemostasis is achieved, this will conclude the visit.

If at the 2 week follow-up the patient has an elevated post-void residual (PVR) <350cc and is symptomatic or if the patient has a PVR > 350 cc and is non-symptomatic, the patient may be placed on either clean intermittent catheterization (CIC), one time straight catheter with close follow-up or indwelling foley catheter. Management for elevated post void residual

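### The protocol both forbids and permits restarting bladder drugs before the month-3 diary, and no analysis rule covers patients who restart; the resulting bias is of unknown, probably small size

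*Combined protocol and SAP*

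**What the plan says.** Two current passages govern oral bladder drugs after injection. Section IV (Methodology) says patients will be "asked to remain off any oral anticholinergic or beta-3 agonist medications, PTNS therapy, or any neuromodulation throughout the entirety of the study". The inclusion criteria in section VI require a two-week washout before enrollment and then add: "May restart antimuscarinics/beta-3 agonists if indicated 6 weeks after Botox injections". Nothing reconciles the two.

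The primary endpoint (section VII, Primary Effectiveness) is at least a 50% reduction in urgency incontinence episodes at 3 months, read from diaries. Scoring depends on that alone: "Patients shall be classified as treatment successes or treatment failures based on this criterion". The month-3 visit has a window of ± 14 days.

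The special scoring rules concern other patients. The text after the sample size tables says: "Patients who exit the study early citing reasons of inadequate urge or incontinence reduction will be included in this analysis as" treatment failures. The intent-to-treat rule covers patients not assessed at 3 months, and the four scenarios under Data analyses vary dropouts only. There is also a completer set: "A completer analysis will be conducted for those who finish the study per protocol".

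Drug use is recorded. For the 3- to 12-month visits, section IV states: "We will also assess for adverse events and concomitant medications at each of these visits". No planned analysis uses that record.

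**The concern.** Baseline is measured off drug, after the washout, but a patient handled under section VI can complete the primary diary on drug. A poor responder to the injection who restarts a tablet and reaches a 50% reduction counts as a success of the injection.

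In a non-inferiority comparison the direction matters. If three sites really work less well, BTX-3 has more failures, so the same rate of rescue by drug adds more successes to that arm. The difference narrows, and a truly inferior technique passes more easily. Providers may also follow different rules, and it is unclear whether a restarter finished per protocol for the completer set.

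**Working it through.** **Timing.** Three months is about 13 weeks; ± 2 weeks gives weeks 11 to 15. Subtracting 6 leaves 5 to 9 weeks in which a restarted drug could act before the diary.

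**Inputs from section VII.** Margin 0.15; one-sided error 0.025; 89 per arm; BTX-10 rate 0.85; BTX-3 rate 0.85 under the alternative and 0.70 at the margin.

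**The plan's own figure.** n = (1.960 + 0.842)² × (2 × 0.85 × 0.15) / 0.15² = 88.95, so 89 per arm, as stated. The probability of declaring non-inferiority is

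Φ( (p3 - p10 + 0.15) / √[p3(1 - p3)/89 + p10(1 - p10)/89] - 1.96 ).

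It equals 80.0% at 0.85 vs 0.85 and 2.5% at 0.70 vs 0.85.

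**Drug conversion.** Let r be the share of injection failures who become diary responders through a restarted drug. It is the share of failures who restart in time multiplied by the share of those who reach a 50% reduction. The documents give neither, so r is an assumption. At the margin, p3 = 0.70 + 0.30·r3 and p10 = 0.85 + 0.15·r10. With equal r the deficit is 0.15(1 - r).

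| r, both arms | p10 | p3 | Deficit | False non-inferiority |
|---|---|---|---|---|
| 0 | 0.850 | 0.700 | 0.150 | 2.5% |
| 2% | 0.853 | 0.706 | 0.147 | 2.8% |
| 5% | 0.8575 | 0.715 | 0.1425 | 3.3% |
| 10% | 0.865 | 0.730 | 0.135 | 4.4% |

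Exact binomial enumeration gives 2.6%, 2.9%, 3.4% and 4.6%. As an example of what lies behind r, 25% of failures restarting with 20% of those converting gives r = 5%.

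**Unequal r.** The deficit stays at 0.15 when 0.30·r3 = 0.15·r10, that is r10 = 2·r3. With r3 / r10 of 2% / 4% the error is 2.5% (no bias); with 2% / 6% it is 2.2% (reversed); with 10% / 5% it is 5.7%.

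**Truly equal arms.** With 0.85 in both arms and equal r, both rates rise together and the difference stays at zero. Power moves only from 80.0% to 81.7% at r = 5%.

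**Scoring restarters as failures.** Let h be the share of true responders who restart and are rescored, so each arm's rate is multiplied by (1 - h).

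- h = 5% in both arms: at the margin 0.665 vs 0.8075, error 3.3%; with equal arms 0.8075 vs 0.8075, power 72%.
- h = 0% in BTX-3 and 5% in BTX-10: 0.70 vs 0.8075, error 9.7%.
- h = 5% in BTX-3 and 0% in BTX-10: with truly equal arms 0.8075 vs 0.85, power 48%.

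**Excluding restarters from the completer set.** If a share s of failures in each arm is removed, p3 = 0.70/(1 - 0.30s) and p10 = 0.85/(1 - 0.15s), with arm sizes reduced to match. At s = 10% the rates are 0.722 vs 0.863 and the error is 3.5%. At s = 30% they are 0.769 vs 0.890 and the error is 7.3%.

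**The case against.** The two passages can be read together as a general request with a conditional rescue exception. On that reading the observed diary reflects injection plus whatever rescue followed, which is a legitimate quantity to compare. That is arguable, but the protocol does not say it, and an outcome possibly on drug would still be set against a baseline off drug with no analysis showing how much depends on it.

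The stronger objection concerns size. Section IV describes candidates who have already failed second-line treatment, schedules no visit between week 2 and month 3, and places management of non-responders at 3 months. All this points to a low r, although the and/or in the inclusion criterion admits patients who failed only behavioral care. In patients, the net gain to BTX-3 at the margin is 89 × 0.15 × r: 0.27 at r = 2%, 0.67 at 5% and 1.3 at 10%. This stands.

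A reader might infer that the stated 2.5% error is badly broken. That would take something like r = 20%, which gives 7.6%, and nothing in the documents supports such a value. Nor do they support a fixed direction, since that depends on the ratio of r between arms.

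It is also fair to object that the obvious analytic remedies carry bias of their own. Failure-scoring favours non-inferiority even under equal restart among true responders, and removing restarters from the completer set shrinks a true deficit. Both points stand and shape the fix.

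**Conclusion.** The concern holds as an unreconciled instruction that reaches the primary endpoint and that no analysis rule covers. It should be fixed, but it does not invalidate the design.

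The text conflict and its timing can be read directly from the protocol. The bias is conditional: it favours non-inferiority if BTX-3 is truly worse and conversion is similar in the two arms. The illustrative error of 2.8% to 4.4% rests on assumed r of 2% to 10%, true rates exactly at the margin, and 89 assessed patients per arm. That r is probably small is a judgement from the care pathway, not a figure in the documents.

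It would be tempting to conclude that restarters should be failures in the primary analysis. The documents do not support that. The person injecting knows the arm, since section IV says of the sham procedure: "The provider will verbalize the injection number to the patient whether it is a true injection or not". Unequal restart among true responders could then do more harm (9.7% in the example) than the problem being cured.

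**What to change.** 1. Amend section VI so that antimuscarinics and beta-3 agonists may not be restarted until the diary used for the month-3 endpoint is complete: the second one if two consecutive diaries are averaged, and any repeat diary after UTI treatment. Align the abstinence sentence in section IV with this.
2. Keep the observed diary as the primary scoring.
3. Report restarts before that diary by arm from the concomitant medication data. For a repeat diary, ask about these drugs at the post-UTI visit too; its description says only "At the unscheduled visit AEs will be reviewed and a clinical decision will be made by an investigator", besides the questionnaires and diary.
4. Add one sensitivity analysis that scores such restarters as failures. State that it can also favour non-inferiority, with the figures above (3.3% error and 72% power at 5% in both arms; 9.7% error at 0% vs 5%).
5. Do not exclude restarters from the completer set, and say so under Data analyses.

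The cost is a short amendment, a few analysis sentences and one medication question; 89 per arm stands. The clinical price is that some symptomatic patients wait about 5 to 9 more weeks for oral drugs, longer if the diary is repeated after a UTI. Section IV already asks this of them. Patients who leave because relief is inadequate already have a scoring rule.
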